2. OBJECTIVE AND ENDPOINTS

The objective of this study is to evaluate the efficacy and safety of LESW for the treatment of IC/BPS.

The primary and secondary endpoints are described as shown below:

(1) Primary End-point (1 month)

The efficacy of LESW will be evaluated for:

Net changes of the O’Leary-Sant symptom score from baseline to 1 month after the treatment day.

(2) Secondary end-points

Efficacy

The efficacy of LESW will be evaluated for:

- (1) Net changes of the following parameters from baseline to 1 month after the treatment day: VAS, functional bladder capacity (FBC), voiding frequency at daytime and voiding frequency at night time as recorded in 3-day voiding diary.
- (2) Global response assessment (GRA) of therapeutic result by the patient (categorized from -3 to +3, indicating markedly worse to markedly improved) at 3 months after the treatment day.
- (3) Net changes of the maximum flow rate, voided volume, and PVR from baseline to 1 month after the treatment day.

(4) Changes of urinary nerve growth factor and cytokines level from baseline to 1 month after treatment day.

Effectiveness of treatment was considered if the patient has an improved GRA by 2 scales at the end-point assessments.

Safety

(1) Local adverse event incidences (hematuria, miction pain, UTI, urinary retention). The severity of adverse event is categorized as indicated below:

Severity of AE	Description
Mild	Transient and easily tolerable, not affecting usual daily activities
Moderate	Causes patient's discomfort, interrupting usual daily activities
Severe	Causes considerable interference with daily activities and may be incapacitating or life-threatening

(2) Systemic Adverse Events:

Any systemic adverse event occurring after LESW will be asked to report and patients will be properly investigated and treated. The cause for systemic adverse event may be not related with LESW.

(3) Changes in physical examinations.

(4) Changes in blood pressure and other laboratory test results will be examined if patients have severe adverse events or physical examinations reveal abnormalities.

(3) Follow-up (3 months)

Efficacy

The efficacy of LESW will be evaluated for:

- (1) Net changes of the following parameters from baseline to 1 month after the treatment day: VAS, functional bladder capacity (FBC), voiding frequency at daytime and voiding frequency at night time as recorded in 3-day voiding diary.

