3. SHOCK WAVE MACHINE AND PROCEDURES

The shock wave applicator (“LITEMED” LM-ESWT-mini system, Taiwan) will be gently placed directly on the ultrasound transmission gel over the skin surface of suprapubic region above the urinary bladder during once a week for 4 weeks, with 2000 shocks, frequency of 3 pulses per second, and maximum total energy flow density 0.25 mJ/mm^2 . The current shock wave intensity and number used was modified from previous report [1, 2].

Eligible patients will be assigned a randomization number in sequential order and each of the randomization will determine the allocation of one of the two treatment groups (LESW and Placebo) in 1: 1 ratio as shown below. The LESW and placebo will be controlled by a research assistance who will not evaluate the therapeutic outcome to ensure the double-blind method.

Vital signs (body temperature, blood pressure, heart rate and respiration rate) will be recorded at pre-treatment and 30 minutes following treatment.

The treatment will be carried out in the out-patient clinic. Patient will be stayed in a treatment room and accompanied by a research assistant.

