5.2. Study Visits and Evaluations

5.2.1. Screening Visit (2 weeks before the treatment day)

5.2.1.1 Explain the nature of the study and have patients to read and sign an Informed Consent Form.

5.2.1.2 Screen patients for inclusion/exclusion criteria (section 4.2 and 4.3).

5.2.1.3 Medical History of IC/BPS and previous treatment modalities.

5.2.1.4 Vital signs monitoring and general physical examinations of all systems, EKG examination to rule out abnormal cardiac diseases, and biochemistry examinations including CBC, PT, APTT, ALT, AST and Cr.

5.2.1.5 Check Uroflowmetry and record, maximum flow rate, voided volume and PVR volume.

5.2.1.6 Urinalysis for WBC, RBC, PH, Protein, Glucose, Bacteria if patient has symptoms suggestive of urinary tract infection.

5.2.1.7 Physical assessments to exclude bladder outlet obstruction or bladder pathology.

5.2.1.8 Record concomitant medication.

5.2.1.9 Dispense three-day voiding diary to record for 3 days before the treatment day.

5.2.1.10 Record O'Leary-Sant symptom score, VAS.

5.2.1.11 Discontinue all previous IC-related medication.

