5.2.2. Randomization and Treatment Visit (V1, Week 0)

5.2.2.1 Vital signs monitoring, check EKG and biochemistry results and confirm eligibility of patients.

5.2.2.2 A randomization number is given to eligible patient.

5.2.2.3 Inform patient of the possible adverse events.

5.2.2.4 Review three-day voiding diary.

5.2.2.5 Collect 30 ml urine for analysis of the urinary NGF and cytokines levels.

5.2.2.6 LESW given.

5.2.3. Treatment Visit (V2, Week 1, 1 week \pm 3 days after the V1 treatment day)

5.2.3.1 Vital signs monitoring, and confirm eligibility of patients.

5.2.3.2 LESW given.

5.2.4. Treatment Visit (V3, Week 2, 1 week \pm 3 days after the V2 treatment day)

5.2.4.1 Vital signs monitoring, and confirm eligibility of patients.

5.2.4.2 LESW given.

5.2.5. Treatment Visit (V4, Week 3, 1 week \pm 3 days after the V3 treatment day)

5.2.5.1 Vital signs monitoring, and confirm eligibility of patients.

5.2.5.2 LESW given.

5.2.5.3 Dispense three-day voiding diary to record for 3 days before the next visit day.

5.2.6 Evaluation Visit I (V5, 1 week \pm 3 days after the V4 treatment day)

5.2.6.1 Review patients voiding diary for urinary frequency, functional bladder capacity, and record reported VAS, O'Leary-Sant symptom score, and GRA.

5.2.6.2 Vital signs monitoring and record adverse events.

5.2.6.3 Check urinalysis for urinary tract infection if patient has symptoms.

5.2.6.4 Check uroflowmetry for maximum flow rate, voided volume, and PVR volume.

5.2.6.5 Appointment for the next visit at 1 month \pm 3 days after the V4.

5.2.6.6 Dispense three-day voiding diary to record for 3 days before the next visit day.

5.2.6.7 Collect 30 ml urine for analysis of the urinary NGF and cytokines levels.

5.2.7 Evaluation Visit II (Primary end-point, V6, 1 month \pm 7 days after the V4)

5.2.7.1 Review patients voiding diary for urinary frequency, functional bladder capacity, and record reported VAS, O'Leary-Sant symptom score, and GRA.

5.2.7.2 Vital signs monitoring and record adverse events.

5.2.7.3 Check urinalysis for urinary tract infection if patient has symptoms suggestive of urinary tract infection.

5.2.7.4 Perform Uroflowmetry study for maximum flow rate, voided volume and PVR volume.

5.2.7.5 Collect 30 ml urine for analysis of the urinary NGF and cytokines levels.

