- (2) The abnormalities of laboratory test results will be reported by patient list in the patients who have been tested for having severe adverse event.
- (3) The changes in physical examinations will be presented in the by-patient list.
- (4) All statistical tests used will be two-tailed with α = 0.05.

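### Change in physical examination is a safety endpoint and a trigger for further safety review, but no examination is scheduled after screening, and blood pressure recorded in every patient has no planned analysis

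*SAP*

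**What the plan says.** Protocol section 2, under Safety, lists "Changes in physical examinations" as item (3). Item (4) is conditional on it: "Changes in blood pressure and other laboratory test results will be examined if patients have severe adverse events or physical examinations reveal abnormalities". There are thus two routes to a review of blood pressure and laboratory change, a severe adverse event or an abnormal examination.

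SAP 7.2, under the secondary safety endpoints, carries the examination endpoint forward as a listing: "The changes in physical examinations will be presented in the by-patient list". For laboratory results it keeps one route only. Abnormalities are to be "reported by patient list in the patients who have been tested for having severe adverse event". Blood pressure is not named in the SAP.

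The screening visit (Protocol 5.2.1.4) includes "Vital signs monitoring and general physical examinations of all systems", and 5.2.1.7 adds "Physical assessments to exclude bladder outlet obstruction or bladder pathology". The evaluation visits V5, V6 and V7 (5.2.6.2, 5.2.7.2 and 5.2.8.2) specify "Vital signs monitoring and record adverse events" but no examination. Protocol section 3 states that vital signs, blood pressure among them, "will be recorded at pre-treatment and 30 minutes following treatment"; section 5.1 repeats this.

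**The concern.** A change from baseline needs a value after baseline. If the schedule provides none, the SAP listing has nothing planned to show, and the examination route in safety item (4) has no planned input. The review of blood pressure change then depends in practice on the severe-event route, so it covers patients selected by outcome. Yet blood pressure is recorded in every treated patient around the intervention, which would allow an unselected comparison of the arms.

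SAP 7.2 sets out to confirm the safety profile. Two of the safety items meant to support that aim either have no scheduled data (examination) or have complete data with no planned use (blood pressure).

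**Working it through.** No alpha, power or effect size enters this point, and the plan gives no figure to reproduce. The check is a reading of the endpoint lists against the visit schedule.

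**Step 1. Where examinations are scheduled (Protocol 5.2)**

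| Visit | Physical examination listed? | Vital signs listed? | Adverse-event recording listed? |
|---|---|---|---|
| Screening | Yes (5.2.1.4, 5.2.1.7) | Yes | No |
| V1 (first session) | No | Yes | No |
| V2, V3, V4 (sessions 2 to 4) | No | Yes | No |
| V5 (1 week after V4) | No | Yes | Yes |
| V6 (1 month after V4, primary endpoint) | No | Yes | Yes |
| V7 (3 months after V4) | No | Yes | Yes |

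Visits after screening with an examination: 0 of 7. V1 begins before any treatment, so the visits that follow at least one session are V2 to V7, and the count there is 0 of 6. The summary of assessments in section 5.1 does not mention an examination either. Each patient has one scheduled examination, at baseline, and no scheduled value from which to form a change.

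**Step 2. The triggers, side by side**

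| Item | Protocol section 2, Safety (4) | SAP 7.2 |
|---|---|---|
| Laboratory results | Severe event, or abnormal examination | Patients tested because of a severe event |
| Blood pressure | Severe event, or abnormal examination | No item |

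The documents differ on laboratory results. This matters because CBC, clotting, liver enzymes and creatinine are measured at screening with no scheduled repeat, so the trigger alone decides whether any later value exists.

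**Step 3. Blood pressure already collected**

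Inputs: 4 weekly sessions (Protocol sections 1 and 5.2); 2 readings per session (section 3, read as applying to every session); about 50 patients, 25 per group (section 4.1 and SAP 7.4).

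- Sets of readings: 4 × 2 × 50 = 400 at most.
- Within-session changes: 4 × 50 = 200 at most, or 4 × 25 = 100 per arm.

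These are upper limits, reached only if every patient attends every session. None of these values has a planned tabulation.

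**The case against.** The strongest reply is that the plan has other ways to capture safety. Protocol 6.1 defines an adverse event broadly, as a new or worsened condition, and requires all of them to be documented. V5 to V7 record adverse events, section 5.1 has patients asked about pain during treatment, and SAP 7.2 compares adverse-event incidence and severity between treatments. A skin reaction or a symptomatic blood pressure change that is reported would enter that comparison. This stands. A reader might infer from the schedule that local or blood pressure effects could never reach a between-arm comparison; the documents do not support that.

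A reader might also infer that the examination endpoint must be empty and that its trigger can never operate. That is too strong as well. Protocol section 2 says patients with systemic adverse events will be properly investigated, which could include an examination, and the eligibility confirmation at V2 to V4 might involve one although none is stated. A by-patient listing could hold such findings, and the SAP promises no arm comparison for this item. But those data would arise selectively and would not be a planned change from screening.

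Finally, missing analysis is not missing monitoring. Vital signs are listed at all of V1 to V7, so blood pressure is watched in every patient. What is absent is a planned summary.

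**Conclusion.** The point holds in a limited form. A declared safety endpoint has no scheduled post-treatment data (0 of 7 visits after screening). One of the two triggers for blood pressure and laboratory review has no planned input, although the severe-event trigger still works. The two documents give different laboratory triggers. Up to 400 sets of blood pressure readings have no planned analysis. The information lost is unreported or asymptomatic change.

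The conclusion assumes that the visit lists in Protocol 5.2 are complete and that the pre-treatment and 30-minute readings apply at every session. The documents give no severe-event rate, so the number of patients whose blood pressure would be reviewed by that route cannot be stated; the conclusion does not need it. The primary efficacy endpoint and its analysis are untouched. This is an inconsistency that should be corrected, and most of the correction is wording.

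**What to change.** 1. **Blood pressure.** In Protocol section 2, Safety (4), remove the condition as it applies to blood pressure. Add to SAP 7.2 a table by arm, for all treated patients (the population that SAP 7.1 already uses for safety), of the change from pre-treatment to 30 minutes at each of the four sessions. The data are already collected; the cost is one protocol edit, one SAP item and a small amount of extra analysis.

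2. **Examination endpoint and trigger.** Reconcile Protocol section 2, the visit lists in 5.2 and SAP 7.2 in one of two ways.
   - State the existing post-treatment visit at which an examination is recorded, no earlier than after the V6 patient-reported scores. An examination before that point could reveal findings to a blinded patient or investigator (Protocol 3.2) and so affect the primary endpoint. The cost is a schedule change and a few minutes at one visit. The limitation is that findings which resolve within about a month of the last session would be missed.
   - Delete the examination endpoint and its trigger from both documents, and rely on adverse-event reporting. This costs only text.

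3. **Laboratory trigger.** Make the condition the same in Protocol section 2, Safety (4) and SAP 7.2 (2), consistent with the choice made under item 2. This is a wording change only.

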7.3. Estimation of Incomplete Data

Due to this relatively small scale of clinical trial, any incomplete observation will be considered as missing data with no specific estimation for the incomplete data.

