5.3. Withdrawal Criteria

Patients with any of the following conditions may be withdrawn from the trial:

- 5.3.1. Patients decide to withdraw their consent at any time-point.
- 5.3.2. Patients indicate the status of lack of efficacy which is of clinical significance judged by the investigators that may lead to permanent damage to the patients.
- 5.3.3. Investigators consider that there is of safety concerns for the patients to remain in the trial (such as development severe medical disease).
- 5.3.4. Lost of follow-up or death.

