7. STATISTICAL ANALYSIS

7.1. Evaluability

Patients receiving baseline screening and treatment will be considered as intent-to-treat (ITT) population. The ITT population with the following conditions will be considered as per-protocol (PP) population:

- 1. Not taking any prohibited medications
- 2. Fulfilling all entry criteria
- 3. Have treatment visit and post-treatment evaluations on the primary endpoint

The efficacy evaluation will be performed on both the ITT and PP datasets while the safety evaluations will be performed only on the ITT datasets. The primary conclusions will be made for the primary and secondary endpoints on the ITT patients.

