7.2 Analysis

The statistical objective of this study is to demonstrate that the efficacy of LESW is superior to placebo with respect to the decreases of O'Leary-Sant symptom score, VAS, increase in functional bladder capacity and improvement in GRA. The safety profile of LESW or placebo for the either group of intravesical treatment of patients with IC/BPS will also be confirmed.

Primary Efficacy Endpoint

The efficacy of LESW treatment will be evaluated for:

(1) Net change of the O'Leary-Sant symptom score from baseline to 1 month after the treatment day.

Secondary Efficacy Endpoint

The efficacy of LESW will be evaluated for:

- (1)Net change of the following parameters from baseline to 1 month after the treatment day: Visual analog score (VAS) for pain (from 0 to 10), functional bladder capacity (FBC), voiding frequency at daytime and voiding frequency at night time as recorded in 3-day voiding diary.
- (2) Global response assessment (GRA) of satisfaction by the patient (categorized into -3, -2, -1, 0, 1, 2, 3, indicating markedly worse to markedly improved) at 1 month after the treatment day. An improvement of GRA by 2 scales at 1 month is considered effective.
- (3) Net changes of the maximum flow rate, voided volume and PVR from baseline to 1 month after the treatment day.

Voiding frequency at daytime and nighttime is measured as mean of the three-day voiding diary preceding the scheduled visit and the record days are 3 days.

Net change of each efficacy item will be analyzed by paired t-test between baseline and post-treatment in the treatment group and controlled group. The net changes of each efficacy item will be analyzed by ANOVA test to compare between treatment group and controlled groups. The global response assessment by the patients will be analyzed by Fisher exact test between the treatment and controlled groups.

All efficacy variables will be reported of respective point estimated and 95% confidence interval. Comparison tests will be reported of respective p value.

Secondary Safety Endpoints

- (1) Local adverse event incidences (hematuria, micturition pain, UTI, urinary retention) will be reported by both treatment group and controlled group and by physiological systems as appropriate. Incidence of adverse events and the categories of adverse event severity between treatments will be analyzed. The coding system used will be COSTART.

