7.4 Sample Size

The sample size per treatment group is arbitrarily determined to be 25 evaluable patients within the two-year study period. Approximately 50 patients are planned to be enrolled to complete the study.

The design of this study was compared between the two groups. The main evaluation index (O'Leary-Sant score) was set to 8.0 decreased in the treatment group, 5.0 decreased in the control group, SD = 5.0, α = 0.05, power= 0.80, and the total sample size was analyzed by computer:

The sample size of this study is about 25 people in each group, at least 50 people need to reach statistical significance.

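### The ITT primary test is in effect a complete-case ANOVA: patients without a 1-month score drop out of it, their V5 scores go unused, and nothing planned would show whether that matters

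*SAP*

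**What the plan says.** - SAP 7.2 makes change in O'Leary-Sant score from baseline to 1 month the primary endpoint. For the between-arm test it states: "The net changes of each efficacy item will be analyzed by ANOVA test to compare between treatment group and controlled groups". GRA at 1 month is compared by Fisher's exact test.
- SAP 7.3, citing the trial's small size, states that "any incomplete observation will be considered as missing data with no specific estimation for the incomplete data".
- SAP 7.1 defines ITT by baseline screening and treatment, with no post-treatment score required. Per-protocol adds, as its third condition, "Have treatment visit and post-treatment evaluations on the primary endpoint". On which set governs: "The primary conclusions will be made for the primary and secondary endpoints on the ITT patients".
- Protocol 5.2.6 collects the O'Leary-Sant score, VAS, GRA, diary and uroflowmetry at V5, one week after the last treatment. Protocol 5.2.7 repeats them at V6, one month after the last treatment, and labels V6 the primary end-point visit.
- Protocol 5.3 allows withdrawal when "Patients decide to withdraw their consent at any time-point", for "lack of efficacy which is of clinical significance judged by the investigators that may lead to permanent damage to the patients", when "Investigators consider that there is of safety concerns for the patients to remain in the trial", and for loss to follow-up or death.
- SAP 7.4 plans on a primary score that "was set to 8.0 decreased in the treatment group, 5.0 decreased in the control group, SD = 5.0", with 25 evaluable patients per arm, about 50 enrolled and no drop-out allowance.

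**The concern.** A change score needs both ends. With an ANOVA of change and no estimation for incomplete data, an ITT patient without a V6 score cannot enter the primary test. The SAP does not use the term complete case, but no other reading fits. The per-protocol analysis is no check on this, because its third condition removes the same patients. A patient lost between V5 and V6 has a post-treatment score on file that no planned analysis uses.

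Some of the permitted reasons for leaving can be linked to outcome. If they are, the completers in the two arms may no longer be comparable, and the estimate from which the primary conclusion is drawn may be shifted. The same applies to GRA, where a patient without a 1-month rating leaves the Fisher denominator. The plan has nothing that would let a reader tell a harmless case from a distorted one.

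**Working it through.** **Inputs from the documents.** Mean decreases 8.0 and 5.0, SD 5.0, 25 per arm (SAP 7.4); two-sided alpha 0.05 (SAP 7.2).

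**The plan's own figure.** With these inputs the standard error is 5 × √(2/25) = 1.41 and the power of the two-group test is 54.7% (noncentral t), not 80%; 80% needs about 45 per arm. That is a separate issue. It is used here only as the full-data reference.

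**Assumptions (not in the documents).** V5 change has the same means and SD as V6 change; V5-V6 correlation ρ = 0.7; a share f of patients whose V5 improvement is below a cut-off c leave before V6.

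**Formula.** Per arm, the completers' mean improvement rises by

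ρ × SD × f × φ(a) / [1 − f × (1 − Φ(a))], with a = (mean V5 improvement − c) / SD.

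**One rule in both arms, c = 0 (non-improvers leave).** a = 1.6 for LESW and 1.0 for placebo. If all leave:
- LESW: 3.5 × 0.1109 / 0.9452 = 0.411
- Placebo: 3.5 × 0.2420 / 0.8413 = 1.007
- Completers' difference: 3 + 0.411 − 1.007 = 2.40

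Power and type I error below are from 200,000 simulated trials per setting. The last two columns assume that only LESW non-improvers leave and that both arms truly improve by 5.

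| Share leaving | Drop-out LESW / placebo, one rule | Completers' difference | Power | Spurious difference, LESW-only loss | Type I error |
|---|---|---|---|---|---|
| A tenth | 0.5% / 1.6% | 2.95 | 53% | 0.09 | 5.0% |
| A quarter | 1.4% / 4.0% | 2.88 | 51% | 0.22 | 5.2% |
| Half | 2.7% / 7.9% | 2.74 | 48% | 0.46 | 6.0% |
| All | 5.5% / 15.9% | 2.40 | 39% | 1.01 | 10.3% |

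**Range of the one-rule result.** With ρ from 0.5 to 0.8 the difference is 2.95-2.97 (a tenth) to 2.32-2.57 (all). With V5 means at half to all of the 1-month means and V5 SD 4 to 5, it is 2.95-2.98 to 2.40-2.50.

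**The direction is not fixed.**
- One rule, c = 8, a tenth leave: 3 + 0.147 − 0.126 = 3.02.
- One rule, c = 10, a quarter leave: 3 + 0.385 − 0.268 = 3.12.
- No true effect, placebo loses its best 10% by V5 score: 3.5 × 0.1755 / 0.9 = 0.68 in favour of LESW.
- No true effect, one rule in both arms: no bias; simulated type I error 4.95-5.00%.

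**Loss unrelated to the score.** No bias. If 4 of 25 LESW patients are lost, the standard error is 5 × √(1/21 + 1/25) = 1.48.

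**Using V5.** When leaving depends on the V5 score (c = 0), a likelihood estimate that uses V5 returns 3.00 under the common rule, with power 54%, 54%, 53% and 51%. Under LESW-only loss with no true effect its bias is within 0.005 and its type I error is 4.8-4.9%. When leaving depends on the V6 status itself, it recovers only part: 2.80 against the completers' 2.63 (half leave), and about 2.4 against 2.15 (all leave).

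**GRA, hypothetical counts.** 14/25 against 7/25 gives Fisher p = 0.085. Dropping 4 LESW non-responders (14/21 against 7/25) gives p = 0.017. Dropping 4 placebo non-responders (14/25 against 7/21) gives p = 0.149.

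**The case against.** The strongest reply is that the effect is likely to be small.
- No drop-out rate, V5 mean, correlation or GRA rate is in the documents.
- Short of every non-improver leaving, the one-rule bias is at most 0.26 against a standard error of 1.41, and one-sided loss takes type I error to 6.0% at most. When drop-out tied to the score was set equal in the two arms at 10% or 20%, simulated bias was within 0.06.
- V5 helps only for losses in the roughly three weeks between V5 and V6, after treatment has ended.
- The lack-of-efficacy ground in 5.3 is narrow. Repeat treatment for non-responders comes only after V6 (Protocol section 2, Follow-up, and 5.2.8.6), which is a reason to stay.
- SAP 7.3 gives a reason, small size, so the omission is deliberate.

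Most of this stands, and it limits the weight of the point. It does not answer the point, because the plan would not show whether loss was in fact small or balanced. Small size also argues the other way: with 25 evaluable per arm and about 50 enrolled, any missing V6 score puts the trial below its target.

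A reader might infer that the plan favours LESW, or that blinding and one withdrawal rule guarantee bias toward the null. The documents support neither. Both depend on who leaves and at what level of improvement, as the upward results of 3.02, 3.12 and 0.68 show.

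**Conclusion.** The point holds as a recommended change, not as a fatal flaw. That the ITT primary test is complete-case, that per-protocol loses the same patients, that V5 goes unused and that no sensitivity analysis or tabulation by arm is planned all follow from the text. The size of any bias does not: every figure rests on assumed drop-out, an assumed V5 distribution and an assumed correlation. Within those assumptions, a planned difference of 3.0 becomes 2.95 to 2.40 if V5 non-improvers leave under a common rule. A spurious 0.09 to 1.01 arises if only LESW non-improvers leave under no effect, the upper end being extreme. Loss of placebo improvers would also inflate the difference. Confidence that the gap matters in practice is moderate, because actual loss may be slight.

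**What to change.** Amend 7.2 and 7.3 together; changing 7.3 alone would leave ANOVA as a second, conflicting primary method.

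- **In 7.2:** for continuous endpoints measured at V5 and V6 (O'Leary-Sant score, VAS, diary variables, uroflowmetry, PVR), replace the between-group ANOVA with a likelihood-based repeated-measures model using baseline, V5 and V6 for all ITT patients as randomised. The V6 contrast in change from baseline is the primary estimate. Keep the ANOVA as the complete-case sensitivity analysis.
- **In 7.3:** state that missing V6 values are handled by this model under missing at random. Add one sensitivity analysis assigning no change from baseline to patients with a missing V6 value. Report GRA on observed ratings and, as a sensitivity analysis, with missing 1-month ratings counted as non-response. Tabulate numbers, reasons and timing of missing V6 scores by arm.

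The withdrawal rules are unchanged.

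**Cost.** SAP wording and a little more analysis; V5 is already collected. The model assumes missing at random and recovers only part of the loss when leaving depends on the unseen V6 score. Patients lost before V5 contribute only their baseline, and V5 adds little precision. The no-change and non-response analyses are stress tests, not estimates. With loss unrelated to the score, no-change gives 0.9 × 3 = 2.70 at 10% loss per arm, (21/25) × 8 − 5 = 1.72 if 4 of 25 are lost from LESW only, and 8 − (21/25) × 5 = 3.80 if 4 of 25 are lost from placebo only. Both should be read beside the complete-case result and the tabulation.
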